## 1. INTRODUCTION

This Statistical Analysis Plan (SAP) outlines the statistical methods for the display, summary and analysis of data collected within the scope of the latest version of the ANB019-208 Protocol (Amendment 1, dated 24 September 2021). As with any SAP, the proposed methods and approaches to the data analysis should be deemed as flexible. The analysis of the data should allow changes in the plan to the extent that deviations from the original plan would provide a more reliable and valid analysis of the data. As such, the statistical analysis to a certain degree is iterative since much of the planning is based on assumptions that require verification. The purpose of this plan is to provide general guidelines from which the analysis will proceed. Nevertheless, deviations from these guidelines must be substantiated by a sound statistical rationale.

The SAP should be read in conjunction with the study protocol and the Case Report Forms (CRFs). This version of the SAP has been developed using the final version of the protocol mentioned above and the version of the annotated CRFs dated 22 December 2021.

This study is designed to evaluate the efficacy and safety of ANB019 in the treatment of subjects with Hidradenitis Suppurativa (HS). (See Protocol [Sections 2.1](#) to [2.3](#) for details).

## 2. STUDY OBJECTIVES

### 2.1 Primary Objective

- To evaluate the efficacy of imsidolimab in subjects with HS

### 2.2 Secondary Objectives

- To evaluate the safety of imsidolimab in subjects with HS
- To further determine the efficacy of imsidolimab on HS signs and symptoms in subjects with HS

### 2.3 Exploratory Objectives

- To further evaluate the effect of imsidolimab on HS signs and symptoms, and quality of life in subjects with HS
- To explore the effect of imsidolimab on cutaneous biomarkers
- To test for immunogenicity to imsidolimab
- To describe the pharmacokinetic (PK) profile of imsidolimab in subjects with HS

## 3. STUDY DESIGN

### 3.1 Study Design

This study is a Phase 2, multicenter, randomized, double-blind, placebo-controlled study to evaluate the efficacy and safety of imsidolimab in adult subjects with hidradenitis suppurativa (HS). This study will also characterize the pharmacokinetic (PK) profile of imsidolimab and explore the immune response to imsidolimab in subjects with HS.

To be eligible for this study, subjects must have a clinically confirmed diagnosis of HS with a disease duration of at least 6 months before Day 1. In addition, subjects will have the following characteristics at Screening and Day 1:

- 1) HS lesions present in at least 2 distinct anatomical areas, 1 of which must be Hurley Stage II (i.e., single or multiple, widely separated, recurrent abscesses with tract formation and cicatrization) or Hurley Stage III (i.e., diffuse or near diffuse involvement, or multiple interconnected tracts and abscesses across the entire area);
- 2) total abscess and inflammatory nodule (AN) count of  $\geq 5$ ;
- 3)  $\leq 20$  draining fistulas.

Randomization will be stratified based on Hurley Stage at baseline (Stage II or III).

The maximum study duration per subject is approximately 44 weeks, which includes a screening period of up to 30 days, followed by a 16-week placebo-controlled period, a 16-week treatment extension period, and an 8-week follow up period. The placebo-controlled period ends at Day 113 (Week 16) and the treatment extension period starts when study treatment is administered at the Week 16 visit. Of note, during the extension period all subjects will receive imsidolimab but their treatment will remain blinded.

During the placebo-controlled period, eligible subjects will be randomized (1:1:1) to receive either imsidolimab (at 1 of 2 different regimens) or placebo, subcutaneously (SC) administered on 4 occasions: Day 1, Day 29 (Week 4), Day 57 (Week 8), and Day 85 (Week 12).

The treatment arms during the placebo-controlled period will be as follows:

[figure not shown]
- Imsidolimab 400 mg on Day 1, followed by 200 mg on Days 29, 57, and 85
- Imsidolimab 200 mg on Day 1, followed by 100 mg on Days 29, 57, and 85
- Placebo on Days 1, 29, 57, and 85

During the extension period, all subjects will receive imsidolimab, SC administered on 4 occasions:

- 400 mg dose of imsidolimab on Day 113 for subjects assigned to placebo arm 3A during the placebo-controlled period, followed by 200 mg doses on Days 141, 169, and 197
- 200 mg dose of imsidolimab on Day 113 for subjects assigned to placebo arm 3B during the placebo-controlled period, followed by 100 mg doses on Days 141, 169, and 197
- 200 mg dose of imsidolimab on Days 113, 141, 169, and 197 for subjects assigned to imsidolimab Arm 1 during the placebo-controlled period
- 100 mg dose of imsidolimab on Days 113, 141, 169, and 197 for subjects assigned to imsidolimab Arm 2 during the placebo-controlled period

The overall study design is summarized and illustrated in **Figure 1**.

**Figure 1 Study Schema**

Abbreviations: D, day; SC, subcutaneously; W, week.

a During the placebo-controlled period, subjects will be randomized (1:1:1) to receive either imsidolimab (at 1 of 2 different regimens) or placebo, SC administered on 4 occasions: 1) 400-mg dose of imsidolimab on Day 1, 200-mg dose of imsidolimab on Days 29, 57, and 85; 2) 200-mg dose of imsidolimab on Day 1, 100-mg dose of imsidolimab on Days 29, 57, and 85.

b The placebo-controlled period ends on Day 113 (week 16) visit, before study treatment administration. Pre-dose assessments performed on Day 113 (week 16) will be used to evaluate the primary and secondary efficacy endpoints, as well as the safety, tolerability, and immune response of imsidolimab compared with placebo. The extension period starts when the study treatment is administered on Day 113 (week 16) visit. All subjects will receive imsidolimab SC administered on 4 occasions during the extension period.

c Subjects in Arm 3 randomized to placebo during the placebo-controlled period will be randomized 1:1 to receive either a 400-mg dose of imsidolimab on Day 113, followed by a 200-mg dose on Days 141, 169, and 197; or a 200-mg dose of imsidolimab on Day 113, followed by a 100-mg dose of imsidolimab on Days 141, 169, and 197. Subjects randomized to imsidolimab in Arms 1 and 2 during the placebo-controlled period will continue to receive the same maintenance dose of imsidolimab (200 mg or 100 mg) on Days 113, 141, 169, and 197.

### 3.2 Randomization

On Day 1, after verification that all inclusion and no exclusion criteria have been met, the subjects will be randomized in a 1:1:1 ratio to receive imsidolimab (at 1 of 2 different regimens) or placebo. Subjects randomized to placebo will be randomized in a 1:1 ratio to receive imsidolimab (at 1 of 2 different regimens) in the extension period which begins on Day 113. Randomization will be stratified based on Hurley Stage at baseline (Stage II or III). Subjects who receive the wrong treatment will be analyzed according to the treatment they were supposed to be randomized to in the efficacy analyses; though, in the safety analyses, will be analyzed according to the treatment they actually received.

### 3.3 Hypothesis Testing

The primary analysis for this study is to compare the mean change from baseline in AN count for imsidolimab vs. placebo at Week 16 of the double-blind treatment period, at a two-sided alpha = 0.10 level. The following hypothesis test will be done separately for each imsidolimab dose arm.

$$H_0: \mu_{\text{imsidolimab}} - \mu_{\text{placebo}} = 0 \text{ vs. } H_A: \mu_{\text{imsidolimab}} - \mu_{\text{placebo}} \neq 0$$

Treatment comparisons may be performed for the secondary or exploratory endpoints and will be considered exploratory in nature. Two-sided p-values and 90% confidence intervals will be produced.

### 3.4 Primary Analysis

A primary analysis will be performed when all subjects have completed Week 16 or have exited study prior. The purpose of this primary analysis is to assist AnaptysBio executive management in making decisions for potential future development of this compound. The primary and secondary efficacy endpoints (defined in **Section 6.2**) of this study will be evaluated in the primary analysis. Listings of the primary and secondary efficacy data will also be provided. Subject disposition, demographics and baseline characteristics will be tabulated and listed as detailed in **Section 7.2 and 7.4**. Safety data including adverse events (AEs), exposure, clinical laboratory measures (hematology, biochemistry, and urinalysis), vital signs, and electrocardiograms (ECGs) will be tabulated and listed as detailed in **Section 7.9**.

Only data collected on or prior to the data cut-off date will be included in the primary analysis.

#### Generation of Blinded Reports

In the primary analysis, blinded tables, listings and graphs will be produced by the [REDACTED] study statistician and study programmer based upon dummy randomization codes. Blinded reports may be shared with the study team for review of ongoing data, production of dry run results, or other reasons as [REDACTED] standard operating procedures (SOPs) and AnaptysBio allow.

#### Generation of Unblinded Reports

The subject, clinical site personnel, and AnaptysBio will be unaware of the randomized treatment assigned to a subject. However, the primary analysis itself will be unblinded. Only the Unblinded Statistician and the Unblinded Programmer responsible for the primary analysis will be aware of the treatment assigned to a subject. The Unblinded Statistician and Unblinded Programmer will both be appointed by [REDACTED] a company external to AnaptysBio. The Unblinded Statistician and Unblinded Programmer will not be

involved in writing the SAP, or in decisions about how the statistical analyses will be conducted, or in daily activities of this study other than those involved in preparing and performing unblinded primary analysis; however, these individuals may be involved in the generation of the randomization list for this study. The Unblinded Statistician and Unblinded Programmer will function independently of the investigators and AnaptysBio clinical study team members. All unblinded roles and responsibilities of these individuals, the sources of the unblinded information, and the processes to maintain the blind are detailed in an Unblinded Data Management Plan.

The Unblinded Statistician and Unblinded Programmer will be in possession of unblinding treatment codes produced for the Interactive Web-based Response System, which is used to randomize subjects to treatment. Upon successful generation of the blinded versions of the datasets and analyses, the Unblinded Statistician and Unblinded Programmer will be responsible for generating unblinded datasets and analyses according to this SAP. The unblinded primary analysis results will be provided to a designated member of AnaptysBio executive management by the Unblinded Statistician.

### **3.5 Sample Size**

The primary efficacy endpoint is the change from baseline in AN count at Week 16. The null hypothesis ( $H_0$ ) to be tested is that the mean change from baseline in AN count is the same for imsidolimab and placebo. This will be tested separately for each imsidolimab dose arm. Assuming a common standard deviation (SD) of 8.2, and a 10% dropout rate, an enrollment of 40 subjects (leaving 36 after dropout) in each of imsidolimab treatment arms and 40 subjects (leaving 36 after dropout) in the placebo arm will have at least 80% power to detect the overall treatment effect for a two sample t-test using a 2-sided significance level of  $\alpha=0.10$ , where the difference in the mean change from baseline between the imsidolimab and placebo group is assumed to be 4.9. The common standard deviation assumption was based on the PIONEER 1 study (Kimball 2014). No adjustments to  $\alpha$  are needed in this study for primary analysis or multiple comparisons.

### **3.6 Study Procedures and Schedule of Activities**

Study procedures and their timing are summarized in the Schedule of Activities (**Table 1**).

Abbreviations: ADA, anti-drug antibody; AE, adverse event; AN, abscess and inflammatory nodule; D, day; DLQI, Dermatology Life Quality Index; ECG, electrocardiogram; EOS, end of study; ET, early termination; FSH, follicle stimulating hormone; HiSCR, Hidradenitis Suppurativa Clinical Response; HiSQol., Hidradenitis Suppurativa Quality of Life; HS, Hidradenitis Suppurativa; HS-PGA, Hidradenitis Suppurativa Physician's Global Assessment; IHS4, International Hidradenitis Suppurativa Severity Score System; NRS, Numeric Rating Scale; PGI-B, Patient Global Impression of Better; PGI-C, Patient Global Impression of Change; PGI-S, Patient Global Impression of Severity; PK, pharmacokinetics; SAE, serious adverse event; SC, subcutaneously; SoA, Schedule of Activities; TB, tuberculosis; W, week; WOCBP, woman of childbearing potential.

a All subjects will receive imisidolimab during the extension period starting on Day 113 (Week 16) visit until Day 197 (Week 28) visit. The placebo-controlled period ends on Day 113 (Week 16) visit, before study treatment administration. The extension period starts when the study treatment is administered on Day 113 (Week 16) visit.

b The ET visit will include all procedures to be done at the EOS visit (Day 28) / Week 40 visit.

c If the Fitzpatrick skin type and/or Smoking history are not collected at screening and D1 respectively, they may be collected at any subsequent visit.

d Height to be measured at screening only for subjects.

e Refer to Protocol [Section 8.2.4](#) for details regarding the complete physical examination.

f Refer to Protocol [Section 8.2.5](#) for details and instructions regarding vital signs.

g Refer to Protocol [Section 8.2.6](#) for details and instructions regarding the ECG. In addition to the time points specified in the SoA, ECGs may be performed at any time during the study if in the opinion of the Investigator it is clinically warranted.

h Bidirectional posterior-anterior view and lateral view chest X-ray will be performed at screening. If a chest X-ray was performed within 6 months of screening and no clinically significant abnormality was observed, it can be skipped at screening.

i The FSH testing is performed for women not of childbearing potential who are postmenopausal (at least 12 months of amenorrhea without an alternative medical cause). Additional pregnancy testing may be performed whenever a menstrual cycle is missed or when pregnancy is otherwise suspected. Refer to [Appendix 11](#) for details and instructions regarding clinical laboratory parameters.

j Refer to Protocol [Section 8.1](#) for details and instructions on AN count, draining fistula count, HISCR, Hurley Stage, HS-PGA, IHS4, Pain NRS, PGI-C, PGI-S, DLQI, HS-PtGA, and HiSQoL. From Screening through Week 32, subjects will not be permitted to use any analgesics related to HS pain within 24 hours of a scheduled study visit. Subjects may use analgesics after the questionnaires are completed at the study visit.

k Sample for PK will be collected pre-dose. See Protocol [Table 5](#) for PK and ADA sample collection time points.

l Tape stripping will be performed for all randomized subjects as part of this study (not optional). Tape strips will be collected from non-lesional and lesional skin at Day 1 and Week 16 and from lesional skin at Week 4 and Week 32. Drainage fluid may be collected (optional) at any visit after Screening in which HS lesional drainage is present, and stored for future biomarker analysis.

m Photography (of representative lesion[s], fistulas, and scarring) is an optional procedure for all subjects at each of the specified visits at selected site. Two images from two distinct regions of highest density inflammatory nodules/abscesses/fistulas should be taken at baseline if possible. The anatomic regions should be identifiable from the images. These regions should be recorded and consistently photographed throughout the duration of the study if possible.

n Starting at Day 113 (Week 16), subjects who received placebo during the placebo-controlled period will be randomized 1:1 to receive imisidolimab at 1 of 2 different regimens. Subjects who received imisidolimab during the placebo-controlled period will not be randomized at the Week 16 visit.

o During the placebo-controlled period, subjects will receive either imisidolimab or placebo SC administered as follow according to randomization arm: 1) 400-mg dose of imisidolimab on Day 1; followed by a 100-mg dose of imisidolimab on Days 29, 57, and 85; 2) 200-mg dose of imisidolimab on Days 29, 57, and 85; 3) placebo. The placebo-controlled period ends at the Day 113 (Week 16) visit, before study treatment administration. During the extension period, subjects assigned to imisidolimab during the placebo-controlled period will continue to receive the same maintenance dose of imisidolimab, 200 mg or 100 mg. Subjects assigned to placebo during the placebo-controlled period will receive either a 400-mg dose of imisidolimab on Day 113, followed by 200-mg doses of imisidolimab on Days 141, 169, and 197; or a 200 mg dose of imisidolimab on Day 113, followed by 100-mg doses of imisidolimab on Days 141, 169, and 197.

p At screening, prior medications should be reviewed and documented. Refer to Protocol [Section 6.5](#).

## 4. DATA AND ANALYTICAL QUALITY ASSURANCE

The overall quality assurance procedures for the study data, statistical programming and analyses are described in Everest's SOPs. Detailed data management procedures are documented in the Data Management Plan, Data Validation Check Specifications, and Data Review Plan. Detailed statistical and programming quality control and quality assurance procedures are documented in the Statistical Analysis and Programming Quality Control/Quality Assurance Plan.

The study endpoints and analytic approaches are both prospectively defined and documented in the protocol and in this SAP. The SAP will be finalized prior to the primary analysis data snapshot, and protocol deviations will be identified and decisions for inclusion and exclusion of subjects from the Per-Protocol Analysis Set (**Section 5.4**) will be made prior to the final database lock and data analysis.

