#### 9.4.2 SUBJECT DISPOSITION

A tabular presentation of the subject disposition will be provided. It will include the number of subjects screened, randomized, treated, completed as well as the number of dropouts with reasons for discontinuation, and major protocol deviations or violations.

A listing will be presented to describe dates of screening, assigned treatment, screen failed with reason, completion or early withdrawal, and the reason for early discontinuation, if applicable, for each subject. A list of protocol deviations/violations will be identified and discussed with the Investigator/AnaptysBio in dry run to categorize as major or minor with decisions of exclusion from analysis sets prior to unblinding.

During the COVID-19 pandemic, protocol deviations related to COVID-19 will be documented and information on how they will be handled in the analyses will be detailed in the SAP.

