## 7.3 Deviations

All protocol deviations will be identified and discussed with the Sponsor during the BDRM prior to final database lock. Important protocol deviations for exclusion from the PP Analysis Set will be determined and appropriately categorized in this meeting. These are defined as potential protocol deviations that may significantly affect the reliability of efficacy study data.

All important protocol deviations will be summarized by treatment group and overall subjects for the ITT Analysis Set. All protocol deviations will also be listed.

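### Per-protocol membership may stay open until final database lock, after unblinded Week 16 results have reached a sponsor executive

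*SAP*

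**What the plan says.** Protocol 9.4.2 has deviations discussed with the investigator and sponsor in a dry run, "to categorize as major or minor with decisions of exclusion from analysis sets prior to unblinding".

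SAP Section 4 sets two deadlines in one sentence. For the plan itself: "The SAP will be finalized prior to the primary analysis data snapshot". For per-protocol inclusion and exclusion, decisions "will be made prior to the final database lock and data analysis".

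SAP Section 7.3 gives the second deadline again: "All protocol deviations will be identified and discussed with the Sponsor during the BDRM prior to final database lock". It places the exclusions there too: "Important protocol deviations for exclusion from the PP Analysis Set will be determined and appropriately categorized in this meeting". The BDRM is the blinded data review meeting.

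SAP Section 3.4 puts an analysis ahead of that lock: "A primary analysis will be performed when all subjects have completed Week 16 or have exited study prior". Under Generation of Unblinded Reports it adds: "However, the primary analysis itself will be unblinded". An external unblinded statistician and programmer run it, and the results pass to one designated member of the sponsor's executive management.

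**The concern.** A per-protocol set is informative only if nobody could have chosen its members in the light of the results. Here the exclusion criterion is a judgement. SAP Section 7.3 refers to deviations that could materially affect the reliability of the efficacy data, with no enumerated list, and SAP Section 7.2 leaves COVID-19 reasons open as a possible ground. The sponsor takes part in that judgement. If the meeting is held at the latest date the SAP allows, someone inside the sponsor already holds unblinded Week 16 results, and no text keeps that person out of the decision.

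The likely route is choice of rule rather than choice of subject. Someone who knows only the aggregate result can still influence which kinds of deviation count as important.

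At stake are the per-protocol sensitivity analysis of the primary endpoint (SAP Section 7.5.4) and the per-protocol analyses of four secondary endpoints (SAP Section 7.5): percent change in AN count, HiSCR50, change in HS Pain NRS, and percent change in HS Pain NRS.

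**Working it through.** The plan gives no figure on this point, so the check is mainly of sequence.

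**1. Deadlines side by side**

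| Source | What is fixed | Latest date |
|---|---|---|
| Protocol 9.4.2 | Deviation category and exclusions from analysis sets | Before unblinding |
| SAP 4 | The SAP | Before the Week 16 snapshot |
| SAP 4 | Per-protocol membership | Before final database lock and data analysis |
| SAP 7.3 | Deviations and per-protocol exclusions | Before final database lock |
| SAP 3.4 | Unblinded primary analysis | Run once all subjects have reached Week 16 or left |

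SAP Section 4 distinguishes the Week 16 snapshot from the final lock and attaches per-protocol decisions to the latter. SAP Section 7.3 mentions only the final lock. No section requires per-protocol sign-off before the Week 16 data are unblinded.

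**2. What the Week 16 package needs**

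SAP Section 3.4 says that disposition and baseline data at the primary analysis follow Sections 7.2 and 7.4. Section 7.2 includes the number and percentage of subjects in the per-protocol set and a listing of reasons for exclusion from it. Those outputs cannot be completed unless membership is already decided, yet Sections 4 and 7.3 do not require that until final lock. The SAP noticed the same problem for PK: Section 5.5 substitutes the Safety Analysis Set at the primary analysis. It has no equivalent rule for the per-protocol set.

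Section 7.2 also calls for a listing of stratification factors with treatment assignment. Section 3.4 says that only the two unblinded staff will know individual assignments. The SAP does not say whether that listing is held back from the executive recipient.

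**3. Declared changes**

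SAP Section 8 lists four changes from the protocol: the spelling of the global impression scales, important deviations in place of major violations, a fifth estimand component, and the PGI-C endpoint titles. The second concerns the per-protocol definition itself, but the timing of the decision is not mentioned.

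**4. Timing**

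Inputs are the nominal visit days and windows in the Schedule of Activities: Day 113 (±4) and Day 281 (±5).

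- Nominal: 281 − 113 = 168 days; 168 / 7 = 24 weeks.
- Shortest within windows: (281 − 5) − (113 + 4) = 276 − 117 = 159 days.
- Longest within windows: (281 + 5) − (113 − 4) = 286 − 109 = 177 days.

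This is the interval between two visits for a subject who completes follow-up. It is not the delay between Week 16 results and the per-protocol decision, because the documents give neither of those dates.

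**5. What does not move**

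The primary analysis uses the ITT set, all randomized subjects (SAP Sections 5.1 and 7.5). The sample-size statement (36 evaluable per arm, difference 4.9, SD 8.2, two-sided alpha 0.10) gives 80.7% power with the noncentral t on 70 degrees of freedom, against the stated 80%. It does not use per-protocol membership.

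**The case against.** The strongest reply has four parts.

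- **The firewall.** SAP Section 3.4 limits knowledge of individual assignments to two external staff. It keeps them out of writing the SAP and out of decisions on how analyses are conducted, and it sends results to one person. The meeting that decides membership is blinded. Steering named subjects in or out would need their assignments. This largely stands, and it disposes of one inference a reader might draw, that those deciding exclusions would hold the treatment codes: the documents say the opposite. Two gaps remain. No text bars the executive recipient from the meeting, and the fate of the Week 16 assignment listing is unstated.
- **A latest date is not a schedule.** Final lock is an outer limit, and the blinded dry run that precedes the unblinded Week 16 outputs would be a natural time for the review. This also stands. A reader might infer that the SAP puts the decision after unblinding; it only allows that.
- **The meaning of unblinding.** Protocol 6.3 says the blind is kept throughout the study, Protocol 8.3.3 speaks of the study being unblinded, and Protocol 9.4.11 allows interim efficacy analyses. Unblinding in Protocol 9.4.2 could therefore mean the end of the study, which would remove the conflict with the SAP. That reading is possible, so a flat contradiction is not proved. But Protocol 9.4.2 does not restrict the word, and the SAP itself calls the Week 16 analysis unblinded.
- **Data analysis in SAP Section 4 could include Week 16.** This is weak. The same sentence names the Week 16 snapshot separately, and Section 7.3 names only the final lock.

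It is also fair to say that SAP Section 3.4 does not list per-protocol efficacy analyses among the Week 16 outputs. That does not remove the need for per-protocol counts and exclusion reasons in the disposition outputs.

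**Conclusion.** The concern holds as a gap in timing. The SAP lets per-protocol membership stay open past an unblinded analysis whose results reach a sponsor executive. That is looser than Protocol 9.4.2 on its natural reading, is not declared in SAP Section 8, and does not fit the SAP's own Week 16 disposition outputs.

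The reach is limited to the per-protocol analyses of the primary endpoint and the four listed secondary endpoints. The ITT primary result, alpha and power are unaffected, so the documents do not support any suggestion that the primary conclusion is compromised. Nor do they support quoting 24 weeks as the delay; that is a visit interval. The size of any bias cannot be computed.

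The conclusion assumes that unblinding in Protocol 9.4.2 covers the Week 16 analysis. If it means end-of-study unblinding, the departure from the protocol falls away, but the open window and the mismatch with the Week 16 outputs remain. It also assumes that no document outside this set, such as the Unblinded Data Management Plan, already fixes membership earlier. This is a cheap improvement rather than a threat to the trial's main result.

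**What to change.** Amend SAP Sections 4 and 7.3 so that:

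1. Deviations through Week 16 are reviewed blinded before the Week 16 snapshot is unblinded.
2. Per-protocol membership for Week 16 endpoints is signed off at that review and then frozen.
3. The later meeting deals with extension-period and PK data only.
4. The executive who receives unblinded results takes no part in analysis-set decisions.

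If the sponsor prefers the later date, it should record the departure in SAP Section 8, keep item 4, and state what replaces the per-protocol counts and exclusion reasons in the Week 16 disposition outputs.

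The cost is one planned blinded meeting held earlier, or split in two, and a few sentences of SAP text. No extra subjects or data are needed.
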